5.2 Health Education Control

The group randomized to receive health education will serve as an attention control. The health education control system is designed to deliver general information 3 times per week via auditory content about a variety of health topics including content on exercise and speech enhancement. Participants are provided with illustrations (e.g., types of exercises important for persons with PD) with written instructions to accompany the auditory content. In addition, participants select a topic from 4 content areas: common symptoms, medical conditions, preventive medicine topics, and tips for healthy living with PD. These PD-

specific tips include recommendations to promote effective communication, mobility strategies, such as strategies for moving from lying down to a sitting position, and from sitting to standing position, and tips to help with performance of daily activities including organization of the physical environment and reducing time pressure. Control participants also receive an illustrated booklet demonstrating these strategies and tips.

6. Study Subject Selection

a. Sample Description

We will recruit 104 patients using a protocol similar to what we are using in our ongoing project to reduce falls in veterans with PD (VA RR&D Merit Review; PI: [name]). Specifically, this approach will involve searching the VA's Corporate Data Warehouse (CDW) to identify patients with PD who potentially meet the eligibility criteria (see 6b & 6c). For patients identified this way, data from the medical records will be abstracted. To assess electronic medical records, we will use the CAPRI System, which provides one interface into the VISTA systems within VISN 1. Patients with PD typically have an initial Neurology consultation and then are seen in Neurology Clinic every 6 months. A standardized VA note format is utilized which includes HPI, medications, and detailed neurologic examination at each visit. The initial VA Neurology consultation will be reviewed with as many subsequent clinic notes as needed to establish the diagnosis of PD and responsiveness to dopaminergic therapy. The two most recent Neurology Clinic notes will also be reviewed to determine current medication use and functional status. Pharmacy records will also be reviewed to confirm stability of medication dosage. Also, Primary Care provider notes and any hospital discharge summaries from the previous year will be reviewed for evidence of exclusionary conditions.

b. Subject Inclusion Criteria

Patients with PD who meet eligibility criteria will be recruited into this study. Specific inclusion criteria will include a physician diagnosis of idiopathic PD; at least 2 of the 3 cardinal signs of PD (resting tremor, rigidity, bradykinesia); response to dopaminergic medication; absence of secondary causes of Parkinsonism; Hoehn and Yahr stage 2-3 disease; stable antiparkinsonian medication for at least 2 weeks; hypokinetic dysarthria; and an age of 40 years or older.

c. Subject Exclusion Criteria

Specific exclusion criteria will include a Mini-Mental State examination score lower than 24; a Beck Depression Inventory-II > 24 ; previous laryngeal surgery; a diagnosis of angina pectoris (unless symptomatically resolved post-revascularization); a history of myocardial infarction (MI) within 6 months, or remote (>6 months) MI with current ischemia on exercise stress test; a history of ventricular dysrhythmia requiring current therapy, or current atrial fibrillation without adequate rate control (resting HR <90); participation in a regular exercise program (2 or more times weekly for 30 minutes or longer per session) during the previous 2 months; and presence of other conditions limiting the ability to participate or associated with poor short-term prognosis, for example, severe degenerative joint disease, stroke with severe residual deficits, severe peripheral neuropathy, severe psychiatric illness, advanced cancer, or renal failure on renal dialysis.

7. Data Collection

7.1 Speech Intelligibility

Speech intelligibility has been described as the primary goal of dysarthria treatment (Miller, 2013; Cannito et al., 2012). In the proposed study, speech intelligibility will be measured as the percentage of words

understood from the acoustic recordings of participants. Participants will be recorded while reading a random set of 11 sentences from the Assessment of Intelligibility in Dysarthric Speech Sentence Intelligibility Test (SIT) stimulus bank (Yorkston & Beukelman, 1980). All recordings will be obtained with the use of a head-mounted condenser microphone.

A group of native speakers of American English with no history of speech, language, or hearing disorders or experience rating speech will participate as listeners in an assessment of speech intelligibility. Listeners will be asked to transcribe a single sentence from each study participant's recording. Amplitude-normalized speech stimuli will be played over headphones. Listeners will be asked to orthographically transcribe each sentence to the best of their ability. Their transcriptions will be compared with the actual stimuli to calculate a percentage of intelligibility.

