STUDY PROTOCOL

Principal Investigator: [name]

[contact]

E-mail: [contact]

Protocol Date: 12/21/2020

ClinicalTrials.gov number: NCT04617496

1. Aims/Objectives

The great majority of individuals with Parkinson's disease (PD) develop speech impairments (Ho et al., 1999; Miller et al., 2007; Schalling et al., 2017), most of which are grouped together and called hypokinetic dysarthria. Hypokinetic dysarthria is typically characterized by altered prosody (e.g., reduced loudness and pitch variation), phonation (e.g., breathy or harsh voice), and articulation (e.g., imprecise consonants, centralized vowels) (Fox & Ramig, 1997; Ho et al., 1999; Hillenbrand & Houde, 1996). Changes in speech may appear early in PD (Miller et al., 2008; Rusz et al., 2011; Skodda et al., 2013) and progress in severity over time (Skodda et al., 2013; Skodda et al., 2009; Skodda, Flasskamp, et al., 2011). Further, such changes in speech lead to significant declines in functional communication and quality of life (Miller et al., 2006 & 2007). Pharmacological and surgical interventions that alleviate motor symptoms in PD are largely ineffective or sometimes even detrimental for speech (Ho et al., 2008; Schulz & Grant, 2000). We propose a pilot randomized, controlled trial (RCT) in patients with hypokinetic dysarthria in PD to assess the potential effectiveness of a home-based exercise intervention with interactive automated speech response features that encourage a higher level of speech performance. The overall goal of this project is to determine if this intervention leads to improved global speech function. The results of this project will provide important information that can be used to design a definitive future trial. Our Specific Aims are:

Primary Aim

Specific Aim 1: To determine whether there is a difference in change in speech intelligibility (how well an individual is understood by others) between patients randomized to the intervention program vs. patients randomized to the health education control program.

Hypothesis: Patients in the intervention program will improve in speech intelligibility at 6 months, as compared with patients in the health education control program.

Secondary Aim

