2.3 Hypokinetic Dysarthria in Parkinson's Disease

Nearly 90% of individuals with PD develop speech impairments (Ho et al., 1999; Miller et al., 2007; Schalling et al., 2017), most of which are grouped together and called hypokinetic dysarthria. Hypokinetic dysarthria is typically characterized by altered prosody (e.g., reduced loudness and pitch variation), phonation (e.g., breathy or harsh voice), and articulation (e.g., imprecise consonants, centralized vowels) (Fox & Ramig, 1997; Ho et al., 1999; Hillenbrand & Houde, 1996). Changes in speech may appear early in PD (Miller et al., 2008; Rusz et al., 2011; Skodda et al., 2013) and progress in severity over time (Skodda et al., 2013; Skodda et al., 2009; Skodda, Flasskamp, et al., 2011). For example, imprecise vowel articulation has been shown to be present even in mild stages of PD (Skodda, Visser, et al., 2011) and is a determinant of reduced speech intelligibility (Neel, 2008; Bradlow et al., 1996). Research indicates that such changes in speech lead to significant declines in functional communication (Miller et al., 2006 & 2007).

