2.4 Speech Treatment in Parkinson's Disease

Pharmacological and surgical interventions that alleviate motor symptoms in PD are largely ineffective or sometimes even detrimental for speech function (Pinto et al., 2004; Ho et al., 2008; Schulz & Grant, 2000; Tripoliti et al., 2014). Given the lack of benefit of these medical interventions, behavioral interventions have become the core methods for speech rehabilitation, especially those that facilitate attention to effort, self-monitoring of vocal output, and generalization of treatment effects into improved ability to communicate effectively in daily life (Donovan et al., 2008; Dykstra et al., 2015; Atkinson-Clement et al., 2015).

Behavioral treatments for speech have demonstrated increases in several overall loudness and other voice characteristics (Atkinson-Clement et al., 2015; Broadfoot et al., 2019; Ramig et al., 2018). However, studies of speech intelligibility, an important determinant of communication effectiveness, have some limitations. Observational studies reporting ratings of intelligibility before and after Lee Silverman Voice Treatment (LSVT) by patients and their families with the use of visual analog or ordinal scales have produced equivocal results (Ramig et al., 1994; Ramig et al., 1995; El Sharkawi et al., 2002; Ramig et al., 2004). Further, the subjective ratings used in these uncontrolled studies suffer from measurement bias because the patients and their families were invested in the treatment and were not blinded to pre- and post-treatment conditions (Rosenthal, 1966; Cannito et al., 2012). Two additional stimulus-based, objective scaling studies have been reported but one focused on intelligibility in terms of sounds or isolated words rather than sentences (sentence intelligibility) (Sapir et al., 2007) and the other was limited to the study of a comfortable loudness condition (Ramig et al., 1994) rather than a more natural condition where ambient noise is typically present.

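### Does scoring intelligibility from level-equalised recordings leave the trial unable to see a benefit that comes through louder speech?

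*Combined protocol and SAP*

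**What the plan says.** The combined protocol and SAP has two outcomes. The primary one (section 7.1) is the percentage of words that inexperienced listeners transcribe correctly from recordings of 11 read sentences, made with a head-mounted microphone. On playback the section says: "Amplitude-normalized speech stimuli will be played over headphones". It does not give the type of normalisation, the speaking-level instruction, or whether noise is present at recording or playback. The secondary outcome (section 7.2) is the CETI-M, on which patients rate their effectiveness in 10 speaking situations, noisy places and the telephone among them.

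The background makes loudness relevant. Sections 1 and 2.3 give reduced loudness as the first example of the features of hypokinetic dysarthria. Section 2.4 says behavioural treatments "have demonstrated increases in several overall loudness and other voice characteristics". It also faults one earlier study for using a comfortable-loudness condition "rather than a more natural condition where ambient noise is typically present", and says subjective ratings in earlier uncontrolled studies "suffer from measurement bias because the patients and their families were invested in the treatment and were not blinded" to the treatment phase. Section 1 sets the goal as to "determine if this intervention leads to improved global speech function" and expects the results to "provide important information that can be used to design a definitive future trial".

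**The concern.** Equalising level before playback discards one of the features by which the disorder is defined. If the intervention mainly made patients louder, the primary score could stay flat and only a self-rating could move, although the plan is itself wary of self-ratings. No blinding of participants is stated.

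At stake is the reading of a null primary result. Aim 1 concerns "speech intelligibility (how well an individual is understood by others"), so a null could be taken to mean that patients are no better understood in daily life when the listening test never presented them at their own level. For a pilot that feeds a larger trial the two readings point different ways: one towards dropping the intervention, the other towards changing the outcome.

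**Working it through.** **What normalisation removes.** It removes overall level. It leaves vowel precision, consonant precision, voice quality and pitch variation. Section 2.3 names imprecise vowel articulation as a determinant of reduced intelligibility, and that passes into the score unchanged. Sections 3 and 5.1 describe the intervention as prompting better speech performance through speech-recognition exchanges; neither names loudness as the target. A problem therefore needs three things together, none of them stated: recording in quiet, a gain through level alone, and a null primary result.

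**Whether noise would carry level through.** Assume a voice gain of G dB, recorded noise R dB below speech, and playback noise P dB below the normalised speech. The listener's signal-to-noise ratio is −10 log10(10^(−R/10) + 10^(−P/10)).

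- G = 5, R = 20, P = 5: the ratio goes from 4.86 to 4.96 dB, so 0.09 dB of the 5 dB survives. With P = 0 it is 0.03 dB.
- G = 5, R = 10: 0.28 dB (P = 0) or 0.78 dB (P = 5) survives.
- No playback noise: the ratio rises by the full 5 dB whatever R is. This helps the listener only if the recorded noise is strong enough to limit transcription.

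So the reservation about noise is right: noise present at recording preserves a level gain, and noise mixed in afterwards mostly does not. But the plan describes no playback noise, and R, P and G are all assumptions. The calculation confirms the mechanism and gives no size for this trial.

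**Power.** Inputs from section 8.1: effect size 0.75, 39 per group, α = 0.05 (taken as two-sided), power 90%. The normal approximation gives Φ(0.75 × √(39/2) − 1.96) = Φ(3.31 − 1.96) = 91.2%, and the two-sample t-test gives 90.5%. The stated 90% is reproduced. Section 5 randomises 104, or 52 per arm, where the t-test power is 96.6%.

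Now suppose a share f of the 0.75 acts through level alone and is lost, so that d = 0.75 × (1 − f):

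| f | d | power, 39 per arm | power, 52 per arm |
|---|---|---|---|
| 0 | 0.75 | 90.5% | 96.6% |
| 5% | 0.71 | 87.4% | 94.9% |
| 10% | 0.675 | 83.7% | 92.6% |
| 20% | 0.60 | 74.4% | 85.8% |
| 50% | 0.375 | 37.3% | 47.4% |

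Nothing in the documents fixes f. If the study behind the 0.75 also equalised level, f is zero for planning purposes and the stated power stands as it is. Section 8.1 describes that study's outcome as the same as this trial's primary outcome but does not say how its stimuli were played.

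**What an added outcome would buy.** Mean vocal level over the same sentences could be analysed with the Aim 1 model. At 90% power it would detect a standardised difference of 0.74 with 39 per arm or 0.64 with 52. It needs calibration at 104 × 2 = 208 recordings. Its result would show that patients read more loudly. After a null primary result, whether they were better understood at their natural level would still be untested. Testing that means a second transcription at recorded relative level in a fixed noise: 208 × 11 = 2,288 more transcriptions for one pass, or 11 more listeners if each hears one sentence per recording.

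**The case for a change.** The strongest case for acting is that loudness is central to this disorder by the plan's own account, that calibrated level adds no visit, sentence or listener, and that calibration cannot be supplied after a recording has been made. All of that is true. It also stands that the plan has no objective measure of a gain from level alone, and that section 7.1 states no ambient-noise condition although section 2.4 counts its absence against earlier work.

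Two parts do not stand. The claim that louder speech can register only on the CETI-M goes too far, because changes in articulation and voice quality that come with louder speech still reach the transcription score. The bias argument does not transfer directly either. Section 2.4 criticises ratings in uncontrolled before-and-after studies, whereas here the CETI-M is compared between randomised arms, and the control arm (section 5.2) receives attention at a set frequency and advice on speech and communication. Self-report bias remains possible but is not the weakness that section 2.4 describes.

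Normalising also has something in its favour. Without calibration, recorded level mixes vocal effort with microphone placement and gain settings, and equalising keeps those differences between visits out of the score.

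**Conclusion.** No change follows. No rule or figure in the plan is shown to be wrong. Section 7.1 defines the primary outcome as the percentage of words understood, and the planned procedure measures that in the same way in both arms. A benefit from level alone, recorded in quiet, would be missed by it. That limits what a null result can say and does not bias the comparison. It is met by describing such a result as no gain in level-equalised sentence intelligibility, which is a matter for reporting.

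The recording condition, the type of normalisation and the scoring behind the 0.75 are gaps that a study team can sensibly fill in its working procedures, provided they are the same for both arms and both visits. Whether to measure level as well is a choice of outcome: the cheap version does not answer Aim 1, and the version that does carries a real transcription burden for a pilot.

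The size of any loss is unknown. The table runs from no loss to a fall to 37.3% power with 39 per arm, driven entirely by an assumed share. The conclusion rests on the plan not naming loudness as the trained feature. If it did, the case for an objective level measure would be stronger.

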7.2 Communication Effectiveness Index

Research indicates that the impact of hypokinetic dysarthria in PD goes beyond severity of speech impairment; it reduces the patient's ability to effectively communicate in daily life (Miller et al., 2008; Miller et al., 2006; McNamara & Durso, 2003). In the proposed study, we will measure the Modified Communication Effectiveness Index (CETI-M), a comprehensive patient-reported outcome. Specifically, participants will rate their communicative effectiveness in 10 different speaking situations (e.g., in noisy environments, over the phone) on a 10-point Likert scale, where 1 = not effective and 10 = extremely effective.

8. Statistical Analysis Plan

Primary Aim

Specific Aim 1: Our primary outcome will be the change in speech intelligibility at 6 months. Because each individual contributes up to two values, at baseline and at 6 months, PROC MIXED (SAS) will be used to estimate regression parameters based on a mixed-effects longitudinal model (Diggle et al., 1994) with the use of the REPEATED statement with an unstructured covariance matrix.

Secondary Aim

Specific Aim 2: We will perform univariate analyses based on the Mann-Whitney U test to compare the distribution of change in CETI-M scores from baseline to 6 months in the intervention vs. control group.

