The current proposal is consistent with the VA's national priority of employing telehealth approaches to help increase access to needed health care (Darkins, 2014; Wilkinson et al., 2016). In addition, this proposal addresses an overall area of RR&D interest related to one of the most complex medical conditions increasing in prevalence in veterans, i.e., PD, which is characterized by multiple impairments including hypokinetic dysarthria.

4. Relevance to Veterans Health

Parkinson's disease is the second most common neurodegenerative disorder, affecting over 80,000 veterans treated within the VA Healthcare System. The great majority of these veterans have speech impairments that negatively impact their ability to communicate effectively in daily life. This study will test the hypothesis that a combined speech and exercise intervention will improve speech intelligibility in people with PD and speech impairment. Remotely-delivered intervention programs have the potential to be accessed easily and conveniently by large numbers of people with PD. The findings of this study may help VA clinicians provide optimal care for the many veterans with PD and speech impairment.

5. Study Design

We will conduct a pilot RCT to evaluate the combined speech and exercise intervention program in patients with hypokinetic dysarthria in PD. One hundred four patients with PD will be randomly assigned (1:1) to the 6-month intervention program or the 6-month health education control program. All evaluations will take place at the Jamaica Plain campus of the VA Boston Healthcare System.

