8.1 Power

With the use of a randomized pre-post LSVT design in patients with hypokinetic dysarthria in PD, Cannito et al. (2012) observed an effect size of 0.75 for the outcome speech intelligibility treated as a continuous variable (our primary outcome). With a sample size of 39 participants per group, we will have 90% power ($\alpha=0.05$) to detect this effect size.

9. References

Bradlow A, Torretta G, Pisoni D. Intelligibility of normal speech I: Global and fine-grained acoustic phonetic

talker characteristics. *Speech Commun.* 1996;20:255–272.

Darkins A. The growth of telehealth services in the Veterans Health Administration between 1994 and 2014: A study in the diffusion of innovation. *Telemed J E Health.* 2014;20:761-8.

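### The primary mixed model lists no fixed effects; its natural reading, a free-baseline change contrast, is generally less precise than a baseline-adjusted contrast from the same data

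*Combined protocol and SAP*

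**What the plan says.** The primary analysis takes two sentences in section 8 (Statistical Analysis Plan, Primary Aim, Specific Aim 1). The outcome is given as "Our primary outcome will be the change in speech intelligibility at 6 months". The method follows: "Because each individual contributes up to two values, at baseline and at 6 months, PROC MIXED (SAS) will be used to estimate regression parameters", from a mixed-effects longitudinal model "with the use of the REPEATED statement with an unstructured covariance matrix".

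The section names no group, time or group-by-time term, no covariate and no contrast to be tested. It does not say whether the baseline means are free by arm or held equal.

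Section 1 states the aim as "To determine whether there is a difference in change in speech intelligibility" between the randomised arms. Section 5 allocates 104 patients 1:1, which is 52 per arm. Section 8.1 says that an earlier study "observed an effect size of 0.75 for the outcome speech intelligibility treated as a continuous variable" and claims 90% power at alpha 0.05 with 39 per group. It does not give the unit of the 0.75 and does not refer to the mixed model.

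**The concern.** When baseline is one of two repeated responses, at least two models fit the text.

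- **Model A (free baseline):** group, time and group-by-time, with a separate baseline mean in each arm. With complete data its group-by-time contrast is exactly the unadjusted difference in mean change.
- **Model B (common baseline):** one baseline mean for both arms and separate 6-month means. Its contrast is in effect the 6-month difference adjusted for baseline. Randomisation justifies the common mean, because any baseline difference between arms is due to chance.

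Section 1's wording about a difference in change makes A the natural reading, although nothing excludes B. Under randomisation both estimate the same effect without bias, and neither raises a type I error concern. What differs is the standard error. A subtracts the whole chance baseline imbalance, and B subtracts only the part that the baseline to 6-month relationship supports.

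Precision matters here because of the trial's stated use: "The results of this project will provide important information that can be used to design a definitive future trial". A wider interval than the data require makes the pilot less informative for that purpose.

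**Working it through.** **1. The plan's own figure.** Inputs from section 8.1: effect size 0.75, 39 per group, alpha 0.05. Sidedness is not stated; two-sided is assumed. For a two-sample t test, the noncentrality is 0.75 / sqrt(2/39) = 3.31 with df = 76, and the noncentral t gives power 90.5%. With 38 per group it gives 89.7%, so 39 is the smallest number that reaches 90%. The stated figure reproduces, and it is the power of model A if 0.75 is in SD-of-change units and 39 per arm are complete.

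**2. Variance of the two contrasts.** Take the baseline SD as 1 and the 6-month SD as k, with correlation rho. Per arm, n0 patients have a baseline value and n1 have a 6-month value. Follow-up is missing completely at random and the covariance is treated as known. Then:

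- Var(B) = 2k²(1 − rho²)/n1
- Var(A) = Var(B) + 2(1 − rho·k)²/n0

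The excess is never negative and is zero only when rho·k = 1.

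**3. Numbers.** n0 = 52 follows from 104 randomised 1:1. n1 = 39 is an assumption: the documents give no dropout rate, and 39 is the per-group number in section 8.1. rho and k are not in the documents, so a range is shown.

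Example with k = 1, rho = 0.5: Var(B) = 2 × 0.75/39 = 0.03846. The excess is 2 × 0.25/52 = 0.00962, so Var(A) = 0.04808. The saving is 0.00962/0.04808 = 20%. The SEs are 0.2193 (A) and 0.1961 (B), so the interval is 11% narrower.

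| rho (k = 1, 52/39) | SE, A | SE, B | Variance saved | Interval narrower by |
|---|---|---|---|---|
| 0.3 | 0.2560 | 0.2160 | 29% | 16% |
| 0.5 | 0.2193 | 0.1961 | 20% | 11% |
| 0.7 | 0.1721 | 0.1617 | 12% | 6% |
| 0.8 | 0.1414 | 0.1359 | 8% | 4% |
| 0.9 | 0.1006 | 0.0987 | 4% | 2% |

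With complete data and k = 1, Var(B)/Var(A) = (1 + rho)/2, so the savings are 35%, 25%, 15%, 10% and 5%.

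**4. Unequal SDs (52/39).** At rho 0.5, 0.7 and 0.8, the saving is 8%, 1% and 0% if the 6-month SD is 1.25 times baseline. It is 36%, 31% and 30% if the 6-month SD is 0.8 times baseline.

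**5. Cost of estimating the covariance.** In simulation (100,000 trials per rho, 52/39, k = 1, slope estimated), the savings were 28.6%, 19.5%, 10.9%, 6.7% and 2.8% at rho 0.3, 0.5, 0.7, 0.8 and 0.9. They were 0.9%, 0.1% and −0.2% at rho 0.95, 0.97 and 0.98. Estimation costs about one percentage point at most.

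**6. Coding.** With group and time both as CLASS variables, intercept, time and group-by-time span all four cell means (design rank 4). Dropping the group main effect therefore leaves model A unchanged. Time plus an indicator equal to 1 only for intervention patients at 6 months has rank 3, which is model B.

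**7. ANCOVA.** In one simulated data set with 52 baselines and 39 follow-ups per arm, completers' ANCOVA and the maximum-likelihood common-baseline model both gave 0.59483.

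**The case against.** The strongest reply is that model A is a standard reading of section 8, estimates exactly the aim in section 1, is unbiased and keeps its error rate. On that view the point is a preference for efficiency, of unknown size. Much of this stands. No stated figure is wrong, the text does not exclude model B, and the gain is small at high rho or when rho·k is near 1. What does not follow is that the choice is immaterial. The precision comes from data already collected, at no more than a trivial estimation cost.

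A reader might infer that the trial is underpowered. Suppose 0.75 were in single-visit SD units, rho were 0.3, and there were 39 baselines and 39 follow-ups per arm. Model A would then have 78.9% power against 92.9% for B. The documents do not support this as an expected shortfall. They state neither that unit nor that rho, and 52 per arm are to be enrolled. With the same unit and rho, A has 82.5% with 52 baselines and 39 followed up, and 89.3% with all 52 followed up. The text also leans the other way: section 8.1 ties 0.75 to the primary outcome, which section 8 defines as change. In SD-of-change units A has 90.5% at 39 complete per group and 96.6% at 52.

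**Conclusion.** The primary model is under-specified, and its natural reading forgoes precision that the baseline data can provide. Assuming equal SDs and 39 of 52 followed up per arm, the adjusted contrast saves from about 29% of the variance at rho 0.3 to about 4% at rho 0.9. That narrows the interval by 16% to 2%. The saving can be larger if the 6-month SD is below the baseline SD, and is about zero when rho times the SD ratio is near 1. The documents give no rho, SD or dropout rate, so where this trial falls in the range is unknown.

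The point does not extend to bias, to an inflated type I error or to an error in the 90% power claim. Nor do the documents establish that model A is what the sponsor intends. This is an improvement that should be made, not a flaw that invalidates the analysis.

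**What to change.** In section 8, Specific Aim 1, write out the fixed effects and the primary contrast:

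- Keep PROC MIXED, the REPEATED statement and TYPE=UN.
- Fit time plus an indicator equal to 1 only for intervention patients at 6 months. Its coefficient is the primary estimate: the 6-month between-arm difference under a common baseline mean, which is also the difference in mean change.
- Do not try to impose the constraint by dropping the group main effect from a CLASS group-by-time model, because baseline means then stay free.
- Report the unconstrained change contrast as a sensitivity analysis.

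Baseline-adjusted ANCOVA of the 6-month value is an equivalent alternative when only 6-month values are missing. The mixed model stays within the stated procedure and also keeps a patient who has only a 6-month value. It would also help to state in section 8.1 whether 0.75 is in SD-of-change or single-visit SD units.

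The cost is a few lines of SAP text and one derived variable, with no new data, visits or patients. If a common baseline is already intended, it only has to be written down.
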